6.5.11.5 Examination of Subgroups

The demographics and baseline characteristics, online consumer survey responses, investigator questionnaire responses, and lens performance rating will also be summarized by the following subgroups.

- Alcon: habitual lens group (including Dailies Total® Multifocal, Dailies® Aquacomfort Plus® Multifocal, Air Optix® Plus Hydraglyde® Multifocal)
- Bausch + Lomb: habitual lens group (including Biotrue® ONEday for Presbyopia, ULTRA® for Presbyopia, PureVision®2 for Presbyopia, PureVision for Presbyopia, SofLens® Multi-Focal)
- CooperVision: habitual lens group (including MyDay® Multifocal, Clariti® 1 Day Multifocal, Biofinity® Multifocal, Proclear 1 Day Multifocal, Proclear Multifocal)
- Johnson & Johnson: habitual lens group (including Acuvue® Oasys Max 1-Day Multifocal, 1-Day Acuvue® Moist Brand Multifocal, Acuvue® Oasys Multifocal, Acuvue® Oasys for Presbyopia)

Habitual lens brand is collected at the eye level. If habitual lens brand for both eyes of the subject are different but belongs to the same manufacturer, then the subject will be counted in that manufacturer category. If the habitual lens brands are from different manufacturers, the subject will be included in the 'Other' lens brand category.

- Subgroups from the baseline questionnaire:
 - Dry Eyes: Very dry or somewhat dry
 - Non-Dry Eyes: Not very dry or not at all dry
 - Tired Eyes: All or most of the time, or quite often
 - Non-Tired Eyes: Now and then, or rarely

Page 29 of 44 - CONFIDENTIAL

- Eye Strain: All or most of the time, or quite often
- Non-Eye Strain: Now and then, or rarely
- Blurry/Fluctuating Vision: All or most of the time, or quite often
- o Non-Blurry/Fluctuating Vision: Now and then, or rarely
- o Binge Watcher: Frequently or occasionally
- o Non-Binge Watcher: Rarely or never
- o Computer or Video Gamer: Frequently or occasionally
- Non-Gamer: Rarely or never
- Physically Active: 5+ times per week, or 3-4 times per week
- Non-Physically Active: Once or twice per week or never
- Excessive Digital Device Users Those with a total of 10 or more hours for a, b, e, g combined.
 - a. Work in an office in front of a computer
 - b. Work at home in front of a computer
 - c. Watch TV
 - d. Drive at night (including riding as a passenger)
 - e. Use a smartphone or tablet (e.g. iPad)
 - f. Study or read from a book, magazine, newspaper etc.
 - g. Play electronic games (on any device or system)
 - h. Engage in sports/physical activity
- Non-Excessive Digital Device Users those with a total of less than 10 hours for a, b, e, g combined.
- Subgroups for baseline add power measured at the Screening/Dispensing Visit:
 - High Add (> 1.50D in both eyes)
 - Low Add ($\leq 1.50D$ in both eyes)
 - Mixed Add

Comparisons between subgroup categories from the baseline questionnaire and subgroups of add power (comparing only the high add versus low add) will be made for agreement on each of the statements in the online consumer survey and investigator questionnaire. Analyses comparing these dichotomous subgroups will be conducted using chi-square tests. If 25% or more of the cells have expected counts less than 5, then Fisher's exact test is used instead. Missing data will not be imputed.

Page 30 of 44 - CONFIDENTIAL

6.5.12 Safety Analyses

6.5.12.1 Adverse Events

All adverse events occurring during the study will be recorded and classified to below categories on the basis of MedDRA terminology, the number and percentage of each category will be summarized.

- AEs (NOT Device Related)
- Serious Adverse Events (SAEs) (NOT Device Related)
- Adverse Device Effects (ADE) (Device Related)
- Unanticipated Serious Adverse Device Effects (USADE) (Device Related)
- Anticipated Serious Adverse Device Effects (ASADE) (Device Related)

A treatment-emergent AE (TEAE) is defined as any AE with an onset on or after the date of the first study device use. If the start date of an AE is incomplete or missing, then the AE will be considered as a TEAE unless a partial date shows it as a pre-treatment event. All reported treatment-emergent AEs (TEAEs) will be summarized by the number of subjects reporting AEs, system organ class, preferred term, severity, seriousness, and relationship to study device.

Ocular Adverse events will be summarized as well by the number of subjects/eyes reporting AEs, system organ class, preferred term, severity, and relationship to study device. Ocular adverse events are defined as AEs specified in one or both eyes. Only treatment-emergent adverse events (TEAEs) are included in the summary.

If more than one AE is coded to the same preferred term for a subject, the subject will be counted only once for that preferred term using the most severe and most related occurrence for the severity and relationship to study intervention summaries, respectively.

If the severity of a TEAE is missing, the maximum severity will be assigned to the event for the summaries by severity. The value will be displayed as missing in the data listings.

If the relationship to the study intervention is missing for a TEAE, the event will be considered related to the study intervention for the summaries. The value will be displayed as missing in the data listings.

All information pertaining to AEs noted during the study will be listed by subject, detailing verbatim given by the investigator, preferred term, system organ class, start date, stop date, severity, actions taken, and device relatedness. The AE onset will also be shown relative (in

Page 31 of 44 – CONFIDENTIAL

number of days) to the day of initial use of the study device. In addition, a list of subjects who experienced SAEs will also be provided.

6.5.12.2 Symptoms/Complaints

Subject symptoms/complaints for each eye will be collected at the Screening/Dispensing Visit and at follow-up visits. Symptoms/complaints collected at the Screening/Dispensing Visit will refer to the habitual lenses; symptoms/complaints collected at follow-up visits will refer to the study lenses. Subjects that experienced any symptoms/complaints will indicate the symptom/complaint level on the following scales:

- 0 None
- 1 Slight symptoms. The symptom is felt or noticed occasionally.
- 2 Mild symptoms. The symptom is noticeable but not irritating or limiting use.
- 3 Moderate symptoms. The symptom is moderately irritating or annoying; the use of device is limited by <25% (short wear time, etc.).
- 4 Severe symptoms. The symptom is very irritating or annoying, and the lens cannot be tolerated.

Symptom	OS (left eye)	OD (right eye)
Discomfort	0-4	0-4
Excessive tearing	0-4	0-4
Photophobia	0-4	0-4
Halos	0-4	0-4
Itching/Burning	0-4	0-4
Spectacle Blur	0-4	0-4
Variable Vision	0-4	0-4
Blurred Vision	0-4	0-4
Lens needs cleaning	0-4	0-4
Handling	0-4	0-4

 Table 2. Symptoms/Complaint Rating Table

Responses will be summarized for baseline and all follow-up visits with frequencies and percentages. Summary will be displayed by visit type (unscheduled/scheduled) and will include a Total column that will summarize the worst case (over scheduled and unscheduled). An additional summary over all follow-up visits will be performed. Symptoms/Complaints will also be summarized categorically by visit, including all follow-up visits category for whether eyes are experiencing problems at any visit in the study. Results will be dichotomized, with 'Absent' if the response is 'None' and 'Present' if the response is other than 'None' for each Symptom.

Individual subject responses for symptoms/complaints parameters will also be presented in subject listings.

Page 32 of 44 - CONFIDENTIAL

6.5.12.3 Slit Lamp Examination

Slit lamp examination (without lenses) will be performed at the Screening/Dispensing Visit and at all follow-up visits.

Epithelial Edema, Epithelial Microcysts, Stromal Edema, Endothelial regularity, Corneal Staining, Limbal Injection, Bulbar Injection, Upper Lid Tarsal Conjunctival Abnormalities, Corneal Neovascularization, and Corneal Infiltrates will be assessment on the following scale:

- Grade 0 = None
- Grade 1 = Trace
- Grade 2 = Mild
- Grade 3 = Moderate
- Grade 4 = Severe

Bulbar Conjunctival Lens Compression/Indentation, New Corneal Scar, and Other Slit-Lamp Findings will be assessed as follows:

- Present
- Absent

All slit lamp measures will be assessed for each eye and will be summarized categorically by visit and visit type (unscheduled/scheduled). Eyes/subjects with multiple visits in a visit category will be counted once for the worst case. The Total column will summarize the worst case (from scheduled and unscheduled visits) for each visit category. In addition, a summary of assessment over all follow-up visits will be provided using the worst case.

A listing of eyes with corneal infiltrates and details of the of corneal infiltrate evaluation will be presented.

A listing of eyes with corneal scars and details of follow-up assessments will be presented.

A subject listing of all slit lamp findings data will also be presented.

6.5.12.4 Best Spectacle Corrected Visual Acuity (BSCVA)

Binocular distance, intermediate, and near high contrast BSCVA (letters correct) will be obtained at the Screening/Dispensing Visit. Binocular distance high contrast BSCVA will be obtained at the Exit Visit as well. Binocular BSCVA in logMAR units will be summarized continuously.

Page 33 of 44 – CONFIDENTIAL

Binocular letter changes from the high contrast distance BSCVA at the Screening/Dispensing Visit to high contrast distance VA for study lenses at all visits will be calculated. Line changes will be summarized categorically using frequencies and percentages. A line change is defined as a change of five letters. Positive line changes reflect improved VA. An additional summary for all study lens assessments will be displayed considering all scheduled visits and unscheduled visit, regardless of the visit window. The worst case will be used for this summary. Details for eyes that decrease two or more lines will be presented. In addition, high contrast distance lens VA will be summarized categorically by visit as to whether the VA is 20/40 or worse in Snellen equivalent units.

Monocular distance high contrast BSCVA will be obtained at the Screening/Dispensing Visit and at the Exit Visit. Monocular BSCVAs will be converted to logMAR score and summarized as continuous statistics at the eye level.

Monocular line changes in BSVCA from baseline to the Exit Visit will be summarized categorically, as well. Details of eyes that decreased two or more lines from the Screening/Dispensing Visit BSCVA to the Exit BSCVA will be tabulated.

Subject listings for binocular and monocular BSCVA will be presented, including letters corrected, VA in logMAR and Snellen equivalent feet unit. In addition, letter changes from baseline BSCVA will also be presented in listings.

6.5.12.5 Exit Eye Examination

Spherocylindrical refraction and keratometry will be assessed at the Screening/ Dispensing and the Exit visit. Spherocylindrical refraction will be measured as sphere (diopters), cylinder (diopters), and axis (degrees) and will be summarized separately as continuous summary statistics in minus cylinder notation (using the same conversion in section 6.5.4), including change from the Screening/Dispensing Visit for sphere and cylinder. The MRSE (diopters) and absolute value of change from baseline will be summarized as continuous measure, and absolute value of change from baseline will also be summarized as a categorical measure using following categories: 0.00-0.99 D, 1.00-1.99 D, 2.00-2.99 D, 3.00-3.99 D, 4.00-4.99 D, and >=5.00 D. MRSE is calculated after converting the sphere and cylinder to minus cylinder notation as MRSE = sphere measurement +1/2 of cylinder measurement. Add power will also be obtained at the Screening/Dispensing Visit and summarized as a continuous measure.

Keratometry will be measured in the horizontal and vertical diopters. The absolute value of keratometry changes collected at the Exit Visit will be summarized both as a continuous and categorical measure, using the following categories: 0.00-0.99 D, 1.00-1.99 D, 2.00-2.99 D,

Page 34 of 44 - CONFIDENTIAL

3.00-3.99 D, 4.00-4.99 D, and ≥ 5.00 D. The horizontal and vertical changes and the largest change over both results will be included in the summary table.

Subject listings of keratometry and spherocylindrical refractive measures will be presented.

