
Statistical Methods:
 
Continuous variables will be summarized using the sample size, mean, standard deviation, median, minimum, and maximum. Categorical variables will be summarized using frequencies and percentages.
 
The responses to the primary endpoint statement will be summarized using categorical summary statistics (strongly agree, agree, slightly agree, neither agree nor disagree, slightly disagree, disagree, strongly disagree).
 
Responses of strongly agree, agree, and slightly agree will be coded to a category "Agree." Responses of strongly disagree, disagree, and slightly disagree will be coded to a category "Disagree." The trichotomized responses will be summarized categorically (agree, neither agree nor disagree, disagree).
 
Neutral responses (i.e., "neither agree nor disagree") will not be included in the primary statistical analysis. The non-neutral responses used for the analysis will be presented using categorical summary statistics (agree, disagree). An exact 95% confidence interval around the proportion of subjects agreeing with the statement will be presented along with the p-value from a one-sided exact binomial test of the alternative hypothesis is that the proportion of subjects agreeing is greater than 0.5.

Sample Size Calculations:
 
Approximately 300 subjects will be enrolled. Allowing for up to 10% losses, power calculations were completed for 270 completed subjects. An exact binomial test with a nominal 5% one-sided significance level will have 93% power to detect the difference between the Null hypothesis proportion, <math>\pi_0</math> of 0.5 and the Alternative proportion, <math>\pi_1</math>, of 0.6 when the sample size is 270.

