### **7.2.2 Clinical Safety Examinations**

Data from the following assessments will be summarized categorically by visit.

- Slit lamp examination
- Symptoms/complaints
- BSCVA in Snellen equivalent units

Data from the following assessments will be summarized using continuous summary statistics.

- Spherocylindrical refraction
- BSCVA in logMAR units

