6.5.4 Demographic and Other Baseline Characteristics

Demographic summaries will be presented for the FAS. Demographic characteristics including age (years), sex, ethnicity, and race will be summarized at the subject level. Age will also be summarized in the following categories: 40 - 49, 50 - 59, 60 - 69, 70+. Subjects reporting more than one race will be summarized as "Multiple." Sex, ethnicity, and race will

Page 14 of 44 – CONFIDENTIAL

be summarized as categorical variables, while age will be summarized as a continuous variable.

Baseline eye characteristic summaries will be presented as continuous statistics summary for the FAS. Diagnostic refraction sphere (diopters), cylinder (diopters) and add power (diopters) will be summarized at the eye level using minus cylinder notation. Positive cylinder will be converted to minus cylinder format by adding the cylinder power to the sphere power, changing the cylinder power sign from '+' to '-', and changing the axis by 90 degrees (adding 90 degrees if axis < 90 and subtracting 90 degrees if axis > 90). The mean refractive spherical equivalent (MRSE) (diopters) will be summarized as a continuous measure. MRSE is calculated after converting the sphere and cylinder to minus cylinder notation as MRSE = sphere measurement +1/2 of cylinder measurement. Axis (degrees) will also be summarized by frequency and percentages in category groups (0, 1 to 30 or 150 to 180, 31 to 59 or 121 to 149, 60 to 120). Pupil size (mm) will be collected at the Screening/Dispensing Visit and summarized continuously as well.

Subject listings for demographic and baseline eye characteristic data will also be presented.

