6.5.10 Analysis of Efficacy

6.5.10.1 Descriptive Statistics

Analyses of effectiveness outcomes will be completed using the Full Analysis Set.

In general, data will be summarized by visit as appropriate. Data will be summarized separately at the subject and eye levels. For lens performance rating endpoints at the subject level, the worst case over both eyes will be derived and summarized for categorical variables.

Summaries for continuous variables will include the sample size (n), mean, standard deviation, median, minimum, and maximum. Means and medians will be presented with one more decimal place than the recorded raw data. Standard deviations will be presented with two more decimal places than the recorded raw data. Minima and maxima will be presented with the same number of decimal places as the recorded raw data. Values with magnitude less than one will be presented with a leading zero to the left of the decimal (e.g., 0.123 or -0.123).

Categorical data will be summarized using frequencies and percentages. Percentages will be presented with one decimal place. Percentages may not be presented when the count is zero. Unless otherwise specified, the denominator for percentages will be the number of non-missing values within the group being presented.

Page 17 of 44 - CONFIDENTIAL

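### SAP 6.5.12.5 summarises cylinder axis as a linear variable; axis is circular, so the tabulated mean can be the perpendicular meridian

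*SAP*

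**What the plan says.** SAP 6.5.12.5 covers two visits: "Spherocylindrical refraction and keratometry will be assessed at the Screening/ Dispensing and the Exit visit". Of refraction it says that sphere, cylinder and "axis (degrees) and will be summarized separately as continuous summary statistics in minus cylinder notation". Change is limited: "including change from the Screening/Dispensing Visit for sphere and cylinder". MRSE and its absolute change are added; change in axis is not.

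The section does not itself mention a mean or SD. Those come from SAP 6.5.10.1: "Summaries for continuous variables will include the sample size (n), mean, standard deviation, median, minimum, and maximum". The protocol synopsis gives the same list. Protocol 7.2.2 puts spherocylindrical refraction under the rule "Data from the following assessments will be summarized using continuous summary statistics" and makes no exception for axis. The output is Table 14.3.6, Safety Analysis Set.

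SAP 6.5.4 treats the Screening axis differently. It tabulates frequencies and percentages "in category groups (0, 1 to 30 or 150 to 180, 31 to 59 or 121 to 149, 60 to 120". One of those groups joins the low end of the scale to the high end. SAP 6.5.12.5 borrows the minus-cylinder conversion from 6.5.4 but not these groups.

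**The concern.** A cylinder axis is a direction without a head or tail. It returns to itself after 180 degrees, so an axis of 1 and an axis of 179 are neighbours. Mean, SD, median, minimum and maximum all assume that the two ends of the scale are far apart. When axes lie on both sides of 0/180, the mean is pulled towards 90, which is the perpendicular meridian, and the SD is inflated.

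At stake is the description of astigmatism at Screening and Exit. The Screening axis has a valid summary in 6.5.4, but the Exit axis has none. The only changes tabulated for refraction are in sphere, cylinder and MRSE, and none of these responds to rotation of a cylinder that keeps its power.

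**Working it through.** The plan gives no figure for axis, so there is none to reproduce. Inputs from the documents are the summary rule (SAP 6.5.12.5 with 6.5.10.1), about 600 eyes (SAP section 4), and exclusion of astigmatism above 1.00 D (exclusion criterion 9). The axis distribution is not given. The distributions in steps 2 and 3 are assumptions.

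**1. Pairs of axes.** For two values a and b, the mean is (a + b)/2 and the SD is |a − b|/√2. The axial mean doubles each angle, averages the unit vectors and halves the resulting angle. With R the length of the mean vector, the axial SD is ½√(−2 ln R), converted to degrees.

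| Axes | Mean and median | SD | Axial mean | Axial SD |
|---|---|---|---|---|
| 5, 175 | 90 | 170/√2 = 120.2 | 180 (= 0) | 5.0 |
| 10, 170 | 90 | 160/√2 = 113.1 | 180 (= 0) | 10.1 |
| 1, 179 | 90 | 178/√2 = 125.9 | 180 (= 0) | 1.0 |

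For 5 and 175, R = cos 10° = 0.985. Under the 6.5.4 groups both eyes fall in the same category.

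**2. All eyes centred on 180, normal spread s (assumed).** Half the eyes fall just above 0 and half just below 180, each as a half-normal. Ignoring rounding, the mean is 90 and the SD is √[s²(1 − 2/π) + (90 − s√(2/π))²]. For s = 15 this is √(81.8 + 78.03²) = 78.6. A simulation of 600 eyes rounded to whole degrees (2,000 runs per row and coding) gives:

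| s | SD by formula | SD simulated | Mean, coded 0–179 | Mean, coded 1–180 |
|---|---|---|---|---|
| 5 | 86.1 | 85.8 | 82.7 | 97.1 |
| 10 | 82.2 | 82.2 | 86.5 | 93.5 |
| 15 | 78.6 | 78.5 | 87.7 | 92.4 |
| 20 | 75.0 | 75.0 | 88.2 | 91.8 |

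The tabulated means are averages over runs. A single run varies more: at s = 5 the 95% ranges are 76 to 89 (coded 0–179) and 90 to 104 (coded 1–180). The median is unstable: at s = 10, coded 0–179, its 95% range is 16 to 159. The axial mean lies on average within 0.7 degrees of 180, and the axial SD returns the spread put in.

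**3. Mixed samples (assumed).** Clusters have a spread of 10 degrees, and 20% of axes are uniform.

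| Near 180 / near 90 | Mean | SD |
|---|---|---|
| 60% / 20% | 89.9 | 67.9 |
| 40% / 40% | 89.8 | 57.3 |
| 20% / 60% | 90.1 | 44.2 |

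The mean is about 90 in all three, so it does not tell opposite patterns apart. The SD differs, but not in a way a reader could interpret.

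**4. Rotation.** If a cylinder of power C rotates by t with sphere and cylinder unchanged, the changes in sphere, cylinder and MRSE are all 0.00 D. The difference cylinder is 2C sin t. At the 1.00 D eligibility limit this is 2 × 1.00 × sin 10° = 0.35 D for 10 degrees, and 2 × 1.00 × sin 30° = 1.00 D for 30 degrees.

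**The case against.** The strongest reply is that very little depends on this. The axis rows of Table 14.3.6 are descriptive, and no hypothesis, endpoint or safety rule uses them. The error also depends on where the axes lie: a cluster near 90 averages correctly. Both points stand.

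A reader might infer that the trial could not detect a rotation of astigmatism. The documents do not support that. The SAP leaves axis out of the change analysis, so the faulty mean is never used to measure change. Refraction is listed by subject, so individual axis shifts can be read. Keratometry change is summarised by meridian, with a detail table at 1 D or more. Monocular BSCVA line change is tabulated, with details of eyes losing ten or more letters. Eligibility caps baseline astigmatism at 1.00 D, which bounds the effect as in step 4. This backstop is partial: listings must be read eye by eye, and neither keratometry nor acuity is refraction.

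A further objection is that the remedies have faults of their own, and this also stands. The 6.5.4 groups keep 0 apart from the group that contains 180, which splits one meridian unless 0 denotes no cylinder; the SAP does not say. Signed power-vector means can cancel: J45 is +0.50 D at axis 45 and −0.50 D at axis 135 for a −1.00 D cylinder, a mean of zero. The fix has to deal with both.

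**Conclusion.** The point holds as a minor error in the plan as written. Followed literally, SAP 6.5.12.5 with 6.5.10.1 produces statistics that are not valid for a circular variable, while SAP 6.5.4 groups the same Screening variable in a way that largely respects its circularity. No assumption about the data is needed for that.

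The size does rest on assumption. A mean of about 83 to 97 and an SD of about 75 to 86 apply if axes centre on 180 with a spread of 5 to 20 degrees. It would be going too far to say that the reported mean must be badly wrong, because the documents do not give the axis distribution; what they support is that it can be.

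The reach is one descriptive safety table. The primary and supportive analyses, MRSE, and the sphere and cylinder summaries are unaffected.

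**What to change.** In SAP 6.5.12.5:

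- Remove axis from the continuous summary and apply the 6.5.4 category groups at both Screening and Exit in Table 14.3.6. Sphere and cylinder stay as planned.
- State whether category 0 means no cylinder. If it does not, merge it with the group that joins 1–30 and 150–180.
- Record in SAP 6.6 that axis departs from the continuous summary in Protocol 7.2.2.

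If a summary of change in astigmatism is wanted, derive for each eye J0 = −(C/2)cos(2 × axis) and J45 = −(C/2)sin(2 × axis). Report the per-eye magnitude of the vector difference, 2√(ΔJ0² + ΔJ45²) in cylinder dioptres, and give the signed components separately for OD and OS. Pooled mean J45 should not stand alone, because it can cancel across mirror-image eyes or opposite rotations. Both components are zero when cylinder is zero, so undefined axes need no special rule here.

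The cost is a little extra derivation from data already collected and one documented change from the protocol. The category change alone is enough to correct the table.
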